5.7.1 Prohibited Interventions

Participation in cognitive interventions aimed toward enhancing or maintaining cognitive abilities will not be allowed. This includes computerized cognitive training or stimulation exercises aimed at countering cognitive decline. Participants will be instructed not to participate in such activities during the entire study period. Formal music training, such as private music lessons or group music classes or courses related to music (as example voice instruction or musical instrument instruction or a music appreciation class), outside of the assigned activities will not be allowed. Individuals who participate in such interventions will be dropped from the study.

⁵ The following sentences were omitted: Each of the conditions will have a textbook and will be assigned weekly homework. Participants will be asked to report the amount of time they spend outside of class completing such activities.

Only data points prior to such participation will be included in analyses. Participant will be deemed ineligible at the time such an incident occurs.

If the participant opts to undergo a surgical procedure that requires general anesthesia or chemotherapy or radiation, we will attempt to complete post-test prior to the surgery or procedure. If the participant undergoes general anesthesia, chemotherapy, radiation, experiences a head injury, stroke, or heart attack, the participant will be withdrawn from the study. All available data points prior to the incident will be used in analyses. The participant will be deemed ineligible at the time of the incident.

Participants will be provided a post-test appointment letter that will include instructions regarding these items when scheduled for post-test. Also, the trainers will remind participants of these instructions on the first day of training.

5.8 Adherence Assessment

To address the study aims, we will use intent-to-treat analyses as detailed in section 9.5 below. We will report the percent of participants who were adherent to the assigned piano training or music instruction exercises. Participants will be considered adherent if they complete at least 80% of the assigned sessions (at least 16 of 20 sessions). The Research Assistant Trainers will record dates that participants attended in-lab training. Participants will be allowed up to 15 weeks to complete the assigned exercises between baseline and post-test.

Primary data analyses will be intent-to-treat. Sensitivity analyses will further examine effects of piano training relative to music instruction among those who were adherent (i.e., who completed 16 or more hours) in both conditions.

08/08/2018

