Both conditions will attend training two times a week for 10 weeks with the goal of completing a total of 20 sessions before post-testing. Participants will be encouraged to complete training two times a week without missing two or more consecutive sessions. Make up sessions will be held for each condition weekly, as needed⁵. The training phase can be extended up to a maximum of 15 weeks, if needed to complete 20 sessions. Participants will be encouraged to complete post-test regardless of intervention adherence. We will code participants as completing training if 16 or more sessions are completed (16 to 20 sessions inclusive). All training sessions must be completed within 15 weeks of training start date. The Trainers will confirm or reschedule the participant to complete an immediate post-intervention assessment within 2-60 days of their final in-lab intervention session (i.e., training completion date), or within 18 weeks of baseline if none of the the intervention phase was completed. See further details below in **Intervention Phase** and **Retention**.

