9.5 Interim Data Analyses

Interim analyses will be conducted in June of 2019, after the pilot, first, and second replicates are completed. We expect that 140 participants will have completed post-test at this time. The purpose will be to confirm feasibility of the training conditions, to assess effect size on cognitive measures from pre- to post- training and adapt number of sessions, if warranted, and to monitor safety.

Interim analyses will be conducted to ensure the safety of the trial. Per NIA, this project does not meet the criteria for requiring a formal Data and Safety Monitoring Plan or Data Safety Monitoring Board because it is not a Phase III clinical trial as defined by NIH. As a behavioral intervention study, this is a phase II efficacy trial¹. At interim analysis, [name] will compare the number of adverse events between the two randomized conditions to assess safety. The two groups will also be compared on attrition rates. Any significant differences between the two conditions in adverse events or attrition rates will be further investigated by [name]. If there is a significant imbalance, confirmed, then [name] will report the findings to the Clinical Trial Coordinator, [name], who is unblinded. The Clinical Trial Coordinator will work with the IRB to decide if the study should be terminated early.

Interim analyses will be conducted to ensure the feasibility of study intervention adherence. If at interim analyses, less than 75% of participants randomized to an arm complete at least 16 sessions (80% of prescribed 20), the intervention arm will be deemed not feasible. If this occurred for both arms, the study will end.

Finally, interim analyses will examine the potential efficacy of the piano training arm. Effect sizes and confidence intervals for all cognitive outcomes will be calculated for pre- to post- training relative to controls. We expect that the piano training arm will produce an improvement of at least $d=0.25$ from baseline to post-test on at least one of the cognitive measures of verbal fluency (phonemic, category or switching), Trails A or B, or Digit Coding, relative to active controls. If an effect size from pre- to post- training relative to controls of this

magnitude is not observed on at least one of these outcomes, we will adapt study procedures by changing the number of training sessions from 20 to 25. In this instance number of training sessions completed will be examined as a covariate in final analyses.

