Specific Aim 2: To examine the moderating effects of MCI on intervention efficacy. We will also test for moderation effects to determine at what stage along the cognitive status continuum—without MCI vs. MCI—intervention is most effective. To do so, we will examine three-way interactions (MCI x training group x time) for the CAP, cognitive, and everyday function composites. When an interaction is significant, we will stratify analyses by MCI status and examine effect sizes. Effect sizes from pre- to post- training relative to controls will be compared for participants with/without MCI. An alpha of .05 will be used for these analyses.

Participants who score 26 or higher on the MoCA will be defined as no MCI (i.e., cognitively normal). Those participants who score a 20-25 on the MoCA will be defined as MCI if they score a 0.5 on the CDR and have performance at or 1 SD below their age, sex, and education norms on any of the following measures: Trails, Verbal Fluency, Digit Coding, Craft Story Recall, Multilingual Naming Test, or Benson Complex Figure. Those with MoCA scores 20-25 who score 0 on the CDR, but have performance at or 1SD below expected for age, sex, and education will be adjudicated prior to analyses. If an individual scores 20-25 on the MoCA, and 0.5 on the CDR, but has performance above expected on all of the aforementioned measures, their case will be adjudicated prior to analyses. The study physicians will adjudicate such cases prior to coding of MCI status for final analyses.

To quantify the effects of piano training further, in addition to examining composite outcomes as detailed above, we will calculate and report effect sizes for pre-to-post change of piano training relative to controls for each individual measure of CAP, cognition, and everyday function for the sample overall as well as stratified by MCI status and among those who were adherent only (80% or more of sessions completed).

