9.8 Exploratory Subgroup Analyses

Pursuant to NIH guidelines on examining sex as a biological variable, we will examine if sex moderates any significant intervention effects identified in aim 1 or aim 2 analyses by examining sex x group x time interactions. Effect sizes will be reported by sex if there are any significant differences (alpha .05).

Relevant to aim 1 and 2 analyses, exploratory analyses will further examine effect size for the pre-to post-change of piano training relative to music listening instruction among those who were adherent (i.e., who completed 80% or more of assigned number of sessions) in both conditions. Analyses detailed above for specific aims 1 and 2 will be repeated among this subsample. Results and effects sizes among the adherent sample will be compared to the ITT derived results and effect sizes.

Relevant to aim 1 and 2 analyses, we will further examine if effects were moderated by a better ear pure-tone average (PTA). In these analyses we will examine if there are significant training group x time x hearing interactions on CAP, cognition, or everyday function, using an alpha of .05.

As it is possible that training will be differentially effective for those with CAP disorders (CAPD), we will identify a subgroup of participants (regardless of MCI status) who could be diagnosed with CAPD. Diagnosis of (C)APD requires performance deficits on the order of at least two standard deviations below the mean on two or more of the following tests^{39, 130}: temporal processing (TCS, ATTR), degraded speech understanding (WIN), or binaural processing (DDT, DST). Analyses for the cognition and everyday function outcomes will be repeated with groups defined as with/without CAPD as an independent variable. We will examine if there are significant training group x time x ADP status interactions using an alpha of .05.

We may also explore moderation effects of covariates such as MCI subtype (amnestic, non-amnestic, multiple domain) to determine who is most likely to benefit from the intervention among participants with MCI. To do so, we will examine three-way interactions (covariate x training group x time) stratified by MCI status, if MCI was a significant moderator in results of analyses for aim 2 described above. Effect sizes will be examined.

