Hearing	-0.09	0.06	.134	-0.14	0.06	.016
Visual acuity	-6.55	5.33	.220	-15.45	5.12	.003
Expectations	-0.79	0.67	.234	-1.96	0.64	.003
	Timed IADL+			Test of Everyday Attention		
Intercept	48.89	1.32	<.001	62.34	1.15	<.001

Group	3.15	2.67	.240	1.37	2.33	.557
Time	0.14	0.79	.863	-8.61	0.67	<.001
Group x time	-1.53	1.58	.327	-0.40	1.340	.765
Hearing	0.07	0.57	.194	-0.02	0.05	.603
Visual acuity	12.75	4.770	.008	0.24	4.470	.957
Expectations	1.02	0.59	.089	-0.79	0.56	.157

Note. ATTR=Adaptive Tests of Temporal Resolution, IADL=instrumental activities of daily living. MCI=mild cognitive impairment. +For ATTR and Timed IADL lower scores reflect better performance.

Table 14.3. *Effect sizes for piano training relative to music listening across composite outcomes and assessments for the analytic sample overall, among those adherent, and by cognitive status.*

Outcome Measure	d Effect Size			
	Overall (n =198)	Adherent (n =189)	Non-MCI (n =146)	MCI (n =52)
Central auditory processing composite	-0.01	-0.01	0.00	-0.07
Dichotic Digits	-0.06	-0.07	-0.03	-0.14
Dichotic Sentence Identification	0.01	0.01	0.02	-0.07
Time Compressed Speech	-0.01	0.01	0.03	-0.06
Words in noise	0.03	0.03	0.12	0.01
Adaptive Tests of Temporal Resolution composite	0.17	0.20	-0.09	0.24
Cognitive composite	-0.03	-0.03	-0.10	0.08
Trails A	0.03	0.06	0.00	0.43
Trails B	-0.17	-0.20	0.01	-0.54
Digit Symbol Coding	0.08	0.09	0.06	0.26
Test of Everyday Attention - Visual elevator timing subtest	0.02	0.02	0.03	0.44
Test of Everyday Attention - Telephone search time	-0.29	-0.32	0.08	-0.27
Verbal fluency composite	0.05	0.06	0.09	-0.12

Letter fluency	0.00	0.02	0.09	-0.36
Category fluency	0.18	0.20	0.18	0.13
Switching fluency	-0.06	-0.05	-0.07	-0.05
Test of Everyday Attention composite	0.04	0.08	-0.30	-0.02
Visual Elevator accuracy	0.01	0.03	-0.12	-0.19
Dual task decrement	0.10	0.13	-0.18	0.22
Timed Instrumental Activities of Daily Living composite	-0.15	-0.21	0.09	-0.13

Note. MCI=mild cognitive impairment. *d* effect sizes were calculated as pre- to post- change in the piano training condition relative to the music listening condition divided by the baseline standard deviation such that positive values would indicate improvement. Adherent analyses include those who completed 15 or more sessions of the assigned condition.

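### The plan sets adherence at 16 sessions (80%) but once says 16 hours (11 sessions), and the reported adherent analysis used 15 sessions (75%) with no recorded change

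*Combined protocol and SAP*

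**What the plan says.** The planned rule is stated five times in the same sense:

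- Section 5.8, first paragraph: "Participants will be considered adherent if they complete at least 80% of the assigned sessions (at least 16 of 20 sessions").
- Section 5.7: "We will code participants as completing training if 16 or more sessions are completed (16 to 20 sessions inclusive").
- Section 9.5, interim feasibility rule: "complete at least 16 sessions (80% of prescribed 20").
- Section 9.6, individual effect sizes: "among those who were adherent only (80% or more of sessions completed").
- Section 9.8, repeat of the Aim 1 and Aim 2 analyses: those "who completed 80% or more of assigned number of sessions".

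Sections 6.1 and 6.1.3 fit this. They tie the training completion date to 16 or more sessions and treat people with 1 to 15 sessions as a separate case.

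Two statements differ. The second paragraph of 5.8, which announces the sensitivity analysis, limits it to those who were "adherent (i.e., who completed 16 or more hours) in both conditions". The note to Table 14.3 in the results says: "Adherent analyses include those who completed 15 or more sessions of the assigned condition".

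**The concern.** Hours and sessions are not interchangeable here, because a session lasts an hour and a half. Read literally, the sentence in 5.8 admits people who attended little more than half the course, while the paragraph above it requires four fifths. The results then use a cut that matches neither.

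The threshold decides who enters the adherent analysis. Section 14 relies on that analysis when it reports that restricting to adherent participants gave the same picture as the primary analysis. Section 9.8 planned that comparison at 80% of assigned sessions. A participant with exactly 15 sessions falls short of completion under 5.7 but counts as adherent in Table 14.3. Section 11 commits the team to documenting any change to the analytic plan with its date and justification, and the log in 11.5 has no entry on adherence.

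**Working it through.** **Inputs.** Session length is 90 minutes = 1.5 h (Section 1.5). The assigned course is 20 sessions (5.7). Section 6.3.4 equates 20 sessions with 30 hours and 25 sessions with 37.5 hours. The adherent sample is 189 and the overall sample 198 (Table 14.3).

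**The plan's own figures reproduce.**
- 0.80 × 20 = 16 sessions, as stated in 5.8 and 9.5.
- 20 × 1.5 h = 30 h and 25 × 1.5 h = 37.5 h, as stated in 6.3.4.

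**The three cuts on one scale.** Hours = sessions × 1.5; share = sessions / 20.

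| Cut | Where | Whole sessions | Hours at that count | Share of 20 |
|---|---|---|---|---|
| 16 sessions | 5.7, 5.8, 9.5 (as 80%: 9.6, 9.8) | 16 | 24.0 | 80% |
| 15 sessions | Table 14.3 note | 15 | 22.5 | 75% |
| 16 hours | 5.8, second paragraph | 11 | 16.5 | 55% |

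For the last row, 16 / 1.5 = 10.67 sessions. Ten sessions give 15.0 h and do not qualify; eleven give 16.5 h and do.

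**What can be said about counts.** The sets are nested: everyone with 16 or more sessions has 15 or more, and everyone with 15 or more has 11 or more. Taking the 189 as a subset of the 198:
- 15 or more sessions: 189 / 198 = 95.5%, leaving 198 − 189 = 9 people below the cut.
- 16 hours or more: between 189 and 198, so at most 9 more than reported.
- 16 sessions or more: at most 189. The documents give no lower bound, because they do not show how many people attended exactly 15 sessions.

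**If the course had been lengthened.** Sections 6.3.4 and 9.5 allow a switch to 25 sessions, for which 80% is 0.80 × 25 = 20 sessions. A definition fixed only at 16 sessions would then be 16 / 25 = 64%. The rule therefore needs to be written as a share of assigned sessions, as 9.8 already does.

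**The case against.** The best reply is that the plan is clear if read as a whole. The first paragraph of 5.8 and four other sections give the same rule, so 'hours' is a slip for 'sessions', and nothing shows that a 16-hour population was intended or used. That stands. A reader might infer that the planned adherent analysis has three competing populations. The documents do not support this: the plan holds two definitions, one of them very probably a drafting error, and the 15-session cut appears only in the results.

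It can also be said that the impact is small. The primary analysis is intent-to-treat, the adherent analysis is labelled sensitivity in 5.8 and exploratory in 9.8, and the group-by-time tests in Section 14 were all non-significant. The 15-session rule is openly stated in the table note. That stands too, and it limits the point to a secondary analysis.

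Finally, the last log entry is dated July 2018, long before the analysis, so the log may simply not have been kept up. That may explain the gap but does not close it: the same document carries the results, and the commitment in Section 11 covers analytic plans as well as procedures.

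The reply leaves two things unanswered. The faulty wording sits in the sentence that defines an analysis population. And the reported cut is looser than the planned one, with no date or reason given.

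**Conclusion.** The point holds as a definition error in the plan plus an undocumented departure in the reported analysis. The plan's rule is 80% of assigned sessions (16 of 20). One sentence in 5.8 instead sets 16 hours, which is 11 sessions or 55%. The reported analysis used 15 sessions, or 75%, with 189 of 198 people.

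A reader might go further and infer that the adherent finding would differ at 16 sessions, or that the cut was loosened to suit the results. Neither is supported. The number with exactly 15 sessions is not given, no result at 16 sessions is shown, and the documents do not say when or why 15 was chosen. The primary result is untouched.

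The conclusion assumes that every session counts as 90 minutes, that the 189 are a subset of the 198, and that the rule in the Table 14.3 note also governed the adherent models. The note is worded for adherent analyses generally, but Supplementary Table B, which Section 14 cites for those models, is not in the document.

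**What to change.** 1. In the second paragraph of 5.8, replace the 16-hour wording with *80% or more of assigned sessions (16 or more of 20)*. This is the sponsor's own rule and stays valid if the assigned number changes.
2. Re-run all adherent results at that cut: the adherent column of Table 14.3 and the adherent models in Supplementary Table B. Re-running the column alone would not test the statement in Section 14 that the adherent results matched the primary ones.
3. Report the adherent number and percent by arm. Section 5.8 promises the percent adherent, and the results text and tables in the document do not give it at 16 sessions.
4. Keep the 15-session version, if wanted, as a labelled post hoc extra, and record the change in the log in 11.5 with its date and reason.

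The cost is a one-line correction, a log entry and a repeat of existing code with a different filter. Section 5.8 has trainers recording attendance dates, so no new data are needed.

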6 CLINICAL AND LABORATORY EVALUATIONS

Schedule of Evaluations

Evaluation	Measure type	Telephone Screening (≤ 60 days)	Baseline	Clinical Evaluation (≤ 45 days)	Randomization ≤3 wks	Intervention Up to 15 wks	Post-Test >2 days and ≤60 days
Informed Consent	R		X				
Inclusion/Exclusion Questionnaire	I/E	X	X	X			X
Geriatric Depression Scale (GDS)	I/E, C		X				
Demographic Data	C		X				
Montreal Cognitive Assessment (MoCA)	I/E, C		X				
Memory Screening History	IV		X				
Hearing and vision screening Pure-tone Hearing Thresholds Speech Recognition Threshold Near Visual Acuity	I/E, C		X				X
Music Reading Assessment	I/E		X				
Central Auditory Processing Time Compressed Speech 65% Words-in-Noise Test Dichotic Digits Test Dichotic Sentence Identification test ATTR	O		X				X

08/08/2018

Evaluation	Measure type	Telephone Screening (≤ 60 days)	Baseline	Clinical Evaluation (≤ 45 days)	Randomization ≤3 wks	Intervention Up to 15 wks	Post-Test >2 days and ≤60 days
Cognitive Assessment Battery Trail Making Test Digit Coding Verbal Fluency - BHR, Clothes/ Girls' Names, Vegetables/ Musical Instruments (baseline) - FAS, Animals/ Boys' Names, Fruits/Furniture (post-test)	O		X				X
Everyday Functional Assessment Timed IADL Test Test of Everyday Attention	O		X				X
Questionnaires Health Questionnaire Medication Audit Health Changes	SC		X X				X
Adverse Events	R		X	X		X	X
Clinical Evaluation NACC assessments: -Clinical Dementia Rating Scale -Craft Story 21 Recall - Immediate and De- layed -Benson Complex Figure Copy and recall -Multilingual Naming Test -Functional Assessment Scale -Clinician Diagnosis form	SC			X			

08/08/2018

Evaluation	Measure type	Telephone Screening (≤ 60 days)	Baseline	Clinical Evaluation (≤ 45 days)	Randomization ≤3 wks	Intervention Up to 15 wks	Post-Test >2 days and ≤60 days
Lab Assessments (upon IRB approval) CBC Metabolic panel Thyroid Stimulating Hormone (TSH) B12 D Folic Acid MRI (if funding acquired)	IV			X			
Randomization	IV				X		
Advanced Measures of Music Audiation (AMMA)- Day 1 of Training	E					X	
Basic Piano Measure (BPM) OR Music Listening Measure (MLM)- At days 1 and 20 of training	E					X	
General Self-Efficacy and Music Performance Self-Efficacy (At days 1 and 20 of training)	E					X	
Intervention sessions	C					X	
NICT Expectations Questionnaire (Between days 17 and 20 of training)	IV, C					X	
Tester blinding assessment	IV						X
C=covariate, E=exploratory, I/E=inclusion/exclusion, IV=internal validity, O=outcome, R=regulatory, SC=sample characterization							

6.1 *Timing of Evaluations*

Prior to Randomization: The baseline visit should be scheduled within 60 days of the telephone screening interview. Informed consent must be obtained first at the baseline study visit prior to any data collection. The GDS, MoCA, Music Reading Assessment, as well as hearing and vision screenings must be completed at baseline, prior to the clinical evaluation. The central auditory processing measures, cognitive assessment battery, everyday functional assessments and health questionnaire should be completed at baseline, but missing items can be administered at the beginning of the clinical evaluation, if needed. The clinical evaluation should be completed within 45 days of the baseline visit completion. The NACC assessments will be completed at the clinical evaluation. All the aforementioned measures for the baseline and clinical evaluations should be completed prior to randomization and must be completed prior to the training content being administered. It will be allowable to administer any of the aforementioned measures that are missing from the baseline or clinical visits after randomization, but administration will not be allowed once the participant has received any piano or music listening training.

Prior to Training Content: Any biomarker assessments must be completed prior to training content (blooddraw, mri, etc.). The general and music self efficacy measures can be administered at either baseline or after randomization on day 1 of training, but must be administered prior to participants receiving any piano- or music listening- content training. If the basic piano or music listening measures are administered prior to randomization, the participant will be withdrawn from the trial and a protocol deviation will be noted. The pre-training basic piano and music listening measures must be administered after randomization and must be administered before training content is delivered. If any of the aforementioned baseline, clinical, or pre-training measures are administered after the training content began, a protocol deviation will be noted. Such measures will be coded as missing and will not be used in analyses.

Intervention Content: The AMMA should be administered on day 1 of training, but it will be allowable to administer the AMMA within the first three training sessions. The NICT questionnaire should be administered between days 17 and 20 of training, but can be administered at the beginning of the post-test visit if it not completed during the intervention phase. The NICT questionnaire must be administered prior to the post-test assessments of CAP, cognition, or everyday function. If the NICT questionnaire is administered after the post-test assessments of CAP, cognition, or everyday function a protocol deviation will be noted. In this instance the NICT questionnaire will be coded as missing and will not be used in analyses. The post-training basic piano measure and music listening measure must be completed after all training content is delivered and prior to the post-test assessment visit. The trainer should confirm with the study coordinator that all scheduled intervention sessions have been completed and the basic piano or music listening assessments are completed prior to the post-test visit. The post-test visit can be rescheduled, if needed, but must occur within 18 weeks of baseline if no intervention was completed, or within 60 days of training completion date (≥ 16 sessions completed). Participant post-tests will be conducted after the intervention phase for those who complete between 1-15 sessions.

⁶ The sentence “Participant post-tests will be conducted after the intervention phase for those who complete between 1-15 sessions” and “(≥ 16 sessions completed)” was added for clarification.

Post-Test Content: The post-training general and music self-efficacy measures must be completed after all training content is delivered, but may be completed at the beginning of the post-test visit, if needed. The post-test assessments of CAP, cognition, and everyday functional measures cannot be completed until after a delay of at least 24 hours after the final intervention session (i.e., training completion date). The post-test assessments of CAP, cognition, and everyday function should ideally take place within 2-30 days of the training completion date (\geq 16 sessions completed). The maximum window for post-test is that it must be completed within 60 days of training completion, or within 18 weeks of baseline if no intervention phase was completed. Participant post-tests will be conducted after the intervention phase for those who complete between 1-15 sessions.⁶

